8.3 Treatment Compliance

8.3.1 Study drugs

Because the attending anesthesiologist will provide the administration of study drugs, treatment compliance is not considered as a potential issue.

8.3.2 Medications susceptible to interfere with outcome measure

8.3.2.1 Opioids

Since opioids have been suggested to inhibit the immune function,⁸⁴ per- and postoperative analgesia will be provided following a **standardized protocol**:

- Fentanyl 2mcg/kg (total dose ranging from 5-10mcg/kg) will be used during surgery
- Surgical wound infiltration with local anesthetics will not be allowed
- Morphine intravenous 0.02-0.04mg/kg for a VAS <4 will be used in the PACU
- Basic postoperative analgesia will be provided using paracetamol and non-steroidal anti-inflammatory drugs
- Subcutaneous morphine 0.1-0.2mg/kg will be prescribed as second line analgesic on the ward (reserve medication)

With the aim to obtain high protocol compliance, postoperative analgesics in USZ will be prescribed in the patient electronic chart (KISIM) following a predefined schema saved in the KISIM database. The attending anesthesiologist has access to the database and will upload this schema to the electronic patient chart, regardless of the assignment group.

For patients enrolled at Klinik Hirslanden, postoperative analgesics will be prescribed using a standardized paper form specifically designed for this study.

8.3.2.2 Glucocorticoids

Glucocorticoids are hardly prescribed in the perioperative setting but can be used as rescue treatment for postoperative nausea and vomiting, in conjunction with other antiemetics. Thus, PONV medication will be administered following a protocol strictly avoiding the use of glucocorticoids.

- Ondansetron amp 4mg intravenous 2x/day (reserve medication)
- Metoclopramid amp 10mg intravenous 3x/day (reserve medication)
- Meclozin supp 20mg intrarectal 1-2x/day (reserve medication)

Postoperative PONV medication will be prescribed in the patient electronic chart (KISIM) following a predefined schema saved in the KISIM database. The attending anesthesiologist has access to the database and will upload this schema to the electronic patient chart, regardless of the assignment group.

For patients enrolled at Klinik Hirslanden, postoperative PONV medication will be prescribed using a standardized paper form specifically designed for this study.

8.4 Prior and Concomitant Therapy

Patients being on any systemic immunosuppressive therapy (glucocorticoids, cytostatics, antibodies, drugs acting on immunophilins, interferon, TNF bindings proteins, mycophenolate), as well as patients taking chronically opioids, planned for pre-operative chemo- or radiotherapy, or undergoing surgery with concomitant

regional anesthesia (epidural catheter, paravertebral blockade, wound infiltration with local anesthetics) will not be included, as these factors are known to interfere with the immune system.^{84,88,89}

Of note is that patients undergoing *intraoperative* radiotherapy with Intrabeam immediately after removal of the tumor are included. This is a new localized intraoperative “standard of care” therapy in breast cancer.

Long-term medications, such as beta-blockers or COX-inhibitors, as well as perioperative blood transfusion or postoperative opioids, have also been suggested to affect the immune system.^{84,87} However, because the benefits of these treatments outweigh their presumable detrimental effect on the immunity, and because strict avoidance of opioids in the postoperative phase would lead to increased pain and distress, these treatments will not be interrupted nor avoided. Opioids will be administered following a strict protocol mentioned previously (8.4.2.1). Adjustment for residual confounders will be performed at the analytical level.

All concomitant and/or rescue treatment(s) have to be recorded in the eCRF, except for perioperative standard medication such as prophylactic antibiotics or heparin.

8.5 Packaging, Labelling and Supply

Both propofol (Propofol-®Lipuro 1% (10mg/ml), B.Braun) and sevoflurane (Sevorane®, AbbVie) are anesthetics used on a daily base in our Anesthesiology department. These products are provided by the Kantonsapotheke and will be labeled as follows:

FOR CLINICAL TRIAL USE ONLY
CTC_BREAST STUDY

Sponsor: [name]
Study ID:
Propofol (B.Braun) OR sevoflurane (AbbVie)
Charge:
Expiry Date:
Storage: at room temperature
Patient ID:

Study products will be stored in a storage facility accessible exclusively to members of the study group. The study investigators will be in charge of the resupply. Regarding the volatile anesthesia, a vaporizer will be filled with sevoflurane and stored in the locker. This vaporizer will be used exclusively for study patients and will be stored back in the locker at the end of the anesthesia.

8.6 Blinding

Adequate double-blinding will be performed: patients will not be told about their group assignments, the surgical team and nurses on the ward will not be informed during

the perioperative period about the anesthesia regimen provided, anesthesia records will be placed in sealed opaque envelopes at discharge from PACU and kept in a secure locker in the anesthesia office until the patient is discharged from the hospital. The pathologist responsible for histopathological assessment, the lab staff performing the CTC detection and the research fellow in charge for isolation and culture of NK cells (outcome assessors) will not have any access to the operation theatre or to the patient chart. The attending anesthesiologist responsible for randomization and providing the anesthesia and collecting the first two blood samples cannot *per se* be blinded but will not participate in any data collection or analysis. The study research team collecting the data will not have access to patient allocation until the final analysis.

In situations requiring a breach in the blinding process, such as the occurrence of SAEs, an Emergency Code Break will be available to the investigator. This Code Break should be opened only in emergency situations when the identity of the investigational product must be known by the investigator in order to provide appropriate medical treatment.

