5.2.3 Other study variables

Demographics and perioperative data will be collected as presented in table 4. Since opioids have been suggested to inhibit the immune function,⁸⁴ perioperative analgesia will be administered following a standardized protocol and will be documented thoroughly. Restriction and stratified randomization are expected to minimize the risk of unbalanced confounders (section 12). However, since we will perform exploratory analyses whenever there is a need to control for residual confounders, the following variables will be collected: hypothermia, blood transfusion, administration of cyclooxygenase inhibitors, beta-blockers, glucocorticoids and date of last menstruation.⁸⁵⁻⁸⁷

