5.2.4 Safety variables

Any adverse event (AE) or serious adverse event (SAE) as described below.

Table 4. Demographics and perioperative data to be collected
Patient data
Age
ASA class
Concomitant therapy
Surgery type
Last menstruation date
TNM stage: size T1-T4; pathological node status N0, N1-3, N>3
Tumor type
Histological tumor grade (grade 1-3)
Receptors (E+/P+; E+/P-; E-/P+; E-/P-; HER2+)
Ki67>35%
Extracapsular tumor spreading
Peroperative data
Anesthesia duration (min)
Mean expiratory fraction in group sevoflurane (Exp%)
Total amount of propofol in group propofol (mg)
Mean BIS value
Total amount of fentanyl (mg)
Mean core temperature (°C)
Administration of b-blockers or COX-inhibitors (yes/no)
Administration of PONV prophylaxis (yes/no)
Blood transfusion (number of units)
Postoperative data
Total amount of morphin in PACU (mg)
Total amount of morphin on the ward (mg)
Administration of b-blockers or COX-inhibitors (yes/no)
Administration of PONV prophylaxis (yes/no)
Blood transfusion (number of units)

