6.4.3 Visit 3 (day of surgery – end of surgery, before extubation)

- Maintenance of anesthesia following the assignment group (sevoflurane or propofol)
- Vital signs will be recorded, concomitant therapy* will be administered
- 2x7.5ml + 2x8ml of blood will be collected and sent for CTC/NK cells assessment (1° variable and 2° variable A)
- Histopathological findings (2° variable B): data related to this endpoint will be collected after completion of the study.
- Perioperative data collection as listed in Table 3
- AE or SAE will be recorded

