10. SAFETY

10.1 Safety Variables

Serious adverse events occurring within the two study groups during the course of the study will be recorded. The attending anesthetist, the surgeon and the nursing staff on the ward will be instructed to report any (S)AE to the investigators of the study. A dedicated study nurse will retrospectively review the chart of patients after hospital discharge to identify any unreported (S)AE.

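### Section 8.6 declares the data collectors blind until the final analysis, but Table 4 has them record two drug-exposure fields named by arm

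*Protocol*

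**What the plan says.** Section 8.6 makes three statements that matter here.

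- On the data team: "The study research team collecting the data will not have access to patient allocation until the final analysis".
- On the attending anaesthesiologist, who randomises and gives the anaesthetic and is acknowledged to be unblindable: this person "will not participate in any data collection or analysis".
- On the anaesthesia records: they go into sealed envelopes on leaving the PACU and are "kept in a secure locker in the anesthesia office until the patient is discharged from the hospital".

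The data to be gathered are fixed in section 5.2.3: "Demographics and perioperative data will be collected as presented in table 4". Among the peroperative items of that table (printed under section 5.2.4) are "Mean expiratory fraction in group sevoflurane (Exp%)" and "Total amount of propofol in group propofol (mg)".

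Section 6.4.3 sets the timing at visit 3 with the instruction "Perioperative data collection as listed in Table 3", and section 6.4.4 repeats it for visits 4 and 5. The table number is a slip: Table 3 summarises NK-cell studies, and the list meant is Table 4.

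On safety, section 10.1 adds: "A dedicated study nurse will retrospectively review the chart of patients after hospital discharge to identify any unreported (S)AE".

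**The concern.** A blinding statement for data collectors is only as good as the forms they handle. If a form has one field that applies to one arm and a second that applies to the other, whoever fills in or reads it learns the treatment. A protocol that still claims blindness until the final analysis then credits the trial with a safeguard it lacks.

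At stake are decisions that involve judgement and are made before the analysis. Section 7.4.1 lets randomised patients be classed as drop-outs and removed from the analysis. Sections 10.1 to 10.4 have a study nurse look for unreported (S)AEs and the investigator judge their relation to the study drug. If those who decide can see the arm, knowledge of treatment can enter both.

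**Working it through.** No arithmetic applies. The check sets the provisions side by side.

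1. **Who is said to be blind, and for how long.** Section 8.6: the team collecting the data, until the final analysis.

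2. **What is collected.** Section 5.2.3 and Table 4: an expiratory fraction tied to the sevoflurane group and a propofol total tied to the propofol group. The trial has two arms, so for a patient treated as randomised exactly one of the two applies. Which one is filled in identifies the drug received.

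3. **Drug received against allocation.** The two coincide except for patients not treated as randomised. Sections 7.4 and 12.3 foresee such patients, so the form discloses treatment received and, for everyone else, allocation.

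4. **When.** Sections 6.4.3 and 6.4.4 place perioperative data collection at visits 3 to 5, between the end of surgery and 72 hours afterwards. Section 12.3 places the analysis after the last patient is enrolled and the study completed. Disclosure therefore comes well before the point that section 8.6 names.

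5. **Who could enter the fields without breaking section 8.6.** The anaesthesiologist knows the drug but may not collect data. Section 13 has the investigators complete one eCRF per participant. No separate unblinded collector, restricted form or deferred entry is described. The protocol leaves nobody who can record these items consistently with its own rule.

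6. **Related provisions.** Section 8.5 puts drug name and patient ID on the same label, in a store open only to the study group. Section 8.8 has the investigator record doses given and individual usage. Section 8.6 gives the investigator an emergency code break, which makes sense only if the investigator is otherwise blind. The anaesthesia record is sealed only up to discharge, and the nurse's chart review in section 10.1 starts after discharge.

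7. **What is shielded.** Section 8.6 keeps the CTC laboratory staff, the NK research fellow and the pathologist away from both theatre and chart. Nothing in steps 1 to 6 reaches them.

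8. **What is left exposed.** The drop-out classification of section 7.4.1, and the finding and causal assessment of (S)AEs in sections 10.1 to 10.4. Section 10.3 names the investigator for causality. Section 7.4.1 does not say who classes a patient as a drop-out; I assume the study team.

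**The case against.** The best defence is that the results that count are protected. The counts and histology come from staff with no access to theatre or chart, and section 12.1 rests its claim against detection bias on participants and outcome assessors, not on data collectors. Section 12 plans no comparative safety test. Most triggers in section 7.4.1 are recorded events, such as a reoperation or a transfer, and surgeons and ward staff are not told the arm. Access rights in an eCRF are often set in data-management documents.

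Most of this stands, and it limits the consequence. It does not remove the contradiction. Inability to follow study procedures still leaves room for discretion in section 7.4.1, and causality is a judgement by definition. A data-management document could restrict access, but section 8.6 as written leaves no permitted person to enter the fields.

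A reader might infer more, and the protocol does not support it:

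- **That the data team opens the anaesthesia record.** This is plausible, since items such as mean BIS and total fentanyl would ordinarily come from it. But section 8.6 does not say who opens the envelope, and section 10.1 speaks only of the chart. The arm-named fields carry the point without it.
- **That every patient's record reveals the allocation.** Only a completed peroperative form does, and it reveals the drug received.
- **That the 10% dropout rate in section 12.5 measures the patients at risk.** It is a general attrition assumption for the sample size, not a forecast of section 7.4.1 removals.
- **That the anaesthesiologist already breaks the rule by drawing samples or reporting (S)AEs.** The same sentence of section 8.6 acknowledges the blood draws, so they are not what it means by data collection. Reporting an event is a safety duty.

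**Conclusion.** The contradiction holds on the explicit text: section 8.6 against Table 4 and the visit schedule. The blinding claimed for the data-collecting team is not delivered by the procedures described.

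The reach is limited. CTC, NK and pathology assessments remain shielded. The exposure is confined to drop-out decisions that take patients out of the analysis and to the finding and causal assessment of (S)AEs. The protocol gives no figure from which the size or direction of a bias could be derived, and none is claimed here.

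The conclusion assumes that those who complete or read the peroperative form belong to the team that section 8.6 calls blind, or make the section 7.4.1 and safety judgements. Sections 8.6 and 13 together point that way. The point merits correction because the remedy is cheap, not because the primary result is shown to be at risk.

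**What to change.** - Put the sevoflurane and propofol exposure fields on a separate eCRF form with restricted access, or defer their entry, until the section 7.4.1 drop-out decisions and the SAE causality assessments are documented and locked.
- Amend section 8.6 to name who may enter these fields. If that is the anaesthesiologist, the bar on data collection needs an exception. State also who has access to the anaesthesia record after discharge.
- Limit the blinding statement to those who are actually blinded. (S)AE review may need the anaesthesia record, since intraoperative events may be documented only there, so whoever reads it should not be described as blind.
- Assign per-protocol status after these decisions are locked, by a rule fixed in advance. It depends on the drug received and cannot be settled without it.
- Correct the references to Table 3 in sections 6.4.3 and 6.4.4 to Table 4.

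The cost is an access setting in the eCRF, a few sentences in the protocol, and separate access for the monitor to verify the restricted form against source.

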8.7 Storage Conditions

Both drugs will be stored in the operation theater, at room temperature, in a storage facility with a secured locker.

8.8 Study Drug Accountability

Investigational product supplies will be kept in a secure, limited access storage area under the recommended storage conditions.

The investigator will maintain accurate and adequate records including dates, lot number, doses given, individual usage, etc.

8.9 Return or Destruction of Study Drug

At the completion of the study, there will be a final reconciliation of drug shipped, drug consumed, and drug remaining. This reconciliation will be logged on the drug accountability form, signed and dated. Any discrepancies noted will be investigated, resolved, and documented prior to return or destruction of unused study drug. Drug destroyed on site will be documented in the study files.

9. STUDY PROCEDURES

9.1 Blood samples for CTC/NK assessment

Blood samples will be collected before induction of general anesthesia (visit 2), at the end of surgery, before extubation (visit 3), 48h (visit 4) and 72h (visit 5) postoperatively.

The CTC detection procedure will be performed as described by the CellSearch® system manufacturer: two 7.5ml samples (i.e. 15ml) of whole blood will be aseptically collected into the CellSave Preservative tubes and will be transported to the University Hospital Zurich; IFA D LAB 26, [name] for subsequent analysis within 96 hours of blood collection.

Assessment of NK cells will be performed at the same 4 pre-definite time points, concomitant to CTC determination, using 2x8ml of peripheral venous blood collected in sterile tubes containing sodium heparin. After subsequent transport to the ZKF, the number of NK cells will be performed using flow cytometry, while NK cells activity will be determined *in vitro* by a direct, cell-based cytotoxicity assay against the K562 (human chronic myelogenous leukaemia) cell line with a fluorescent read-out as previously described.^{82,83}

Tubes for CTC/NK cells detection will be kept in plastic bags specifically labeled with the visit number. Four bags per patient will be available: 2 for the attending anesthetist (visit 2 and 3) and 2 for the attending nursing staff on the ward (visit 4 and 5). The blood samples will be eliminated after subsequent analysis.

9.2 Study drug administration

Sevoflurane or propofol will be administrated according to patient allocation. Because patients scheduled for breast cancer surgery will need a general anesthesia in any case, regardless of their participation to this study, both drugs will be provided by the UHZ.

9.3 Pregnancy test

Patients of childbearing age scheduled for breast surgery are routinely screened for pregnancy one day prior to surgery. After obtaining written informed consent, the attending anesthetist will look for pregnancy test results in the KISIM database. Considered as a routine prescription at the UHZ, the test should not create additional costs.

Patients of childbearing age at Klinik Hirslanden will be screened for pregnancy at enrollment. The UHZ study team will provide the pregnancy tests and will bear the associated costs.

10. SAFETY

10.1 Safety Variables

Serious adverse events occurring within the two study groups during the course of the study will be recorded. The attending anesthetist, the surgeon and the nursing staff on the ward will be instructed to report any (S)AE to the investigators of the study. A dedicated study nurse will retrospectively review the chart of patients after hospital discharge to identify any unreported (S)AE.

10.2 Definition of (Serious) Adverse Events

Adverse events

Adverse events (AEs) are defined as any untoward medical occurrence in a patient or clinical investigation subject administered a pharmaceutical product and which does not necessarily have a causal relationship with this treatment. An AE can therefore be any unfavourable and unintended sign (including an abnormal laboratory finding), symptom, or disease temporally associated with the use of a medicinal study product, whether or not related to the medicinal study product. An AE may also consist of a new disease, an exacerbation of a pre-existing illness or condition, a recurrence of an intermittent illness or condition, a set of related signs or symptoms, or a single sign or symptom.

AEs observed by the investigator and/or reported by the subject must referring to the HFG, not be reported in the eCRF -

All AEs, qualifying as an SAE , observed by investigator must be reported in the eCRF. For all SAE`s sufficient information will be pursued and/or obtained so as to permit an adequate determination of the outcome of the event and an assessment of the casual relationship between the SAE and the investigational drug or study treatment(s). The causality assessment of the event to the study drug will be made by investigator and Sponsor-investigator, based on criteria listed in the ICH guidelines

Whenever available, the underlying disease or condition for which a therapeutic or diagnostic procedure is required should be reported as the AE term. Surgeries or other invasive procedures that had already been planned prior to the start of the study do not have to be documented as AEs. These planned procedures will be recorded in the eCRF by the investigator at the baseline visit. It is not important if the condition was known before enrolment, only if the procedure was planned before.

Pregnancy per se does not classify as an AE. However, AEs related to a pregnancy have to be reported like any other AEs. Pregnancy should be confirmed by a reliable laboratory test. Pregnant subjects must be immediately withdrawn from the clinical study. All pregnancies occurring during the treatment phase of the study and within 30 days after discontinuation of study medication have to be reported to the

Investigator-Sponsor within one working day of the investigational sites knowledge of the pregnancy on the Initial Pregnancy Report Form. The Sponsor-Investigator will contact the attendant physician by phone during pregnancy and after the estimated date of delivery to enquire about course and outcome of the pregnancy. Course of the pregnancy and health status of the new born child have to be documented on the Follow-Up Pregnancy Report Form.

Serious adverse event

An SAE is any untoward medical occurrence that at any dose results in

- results in death,
- is life-threatening,
- requires subject hospitalization or prolongation of current hospitalization,
- results in persistent or significant disability/incapacity, or
- is a congenital anomaly/birth defect,
- any important medical event and any event which, though not included in the above, may jeopardise the subject or may require intervention to prevent one of the outcomes listed above.

Any other medically important condition that may be not immediately life-threatening or results in death or hospitalization but may jeopardize the subject or may require intervention to prevent one of the outcomes listed above should also usually (i.e. based on medical and scientific judgment) be considered serious. For example: intensive treatment at home for allergic bronchospasm; certain laboratory abnormalities (e.g. blood dyscrasias); convulsions that do not result in hospitalisation; development of drug dependency or drug abuse.

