6.3.3 Safety Endpoints

Adverse events (AE) or serious adverse events (SAE) will be actively sought and reported. For comprehensive description of AE/SAE, see paragraph 10 below.

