10.3 Recording of (Serious) Adverse Events

Clinical investigators and ultimately the protocol Principal Investigator (PI) have the primary responsibility for AE identification, documentation, grading, and assignment of attribution to the investigational agent/intervention.

Clinical study subjects will be routinely questioned about AEs at study visits. The well-being of the subjects will be ascertained by neutral questioning ("How are you?"). The investigator is responsible for reporting all AEs occurring during the course of the study.

All observed or volunteered adverse drug events (serious or non-serious) and abnormal test findings, regardless of treatment group or suspected causal relationship to the investigational drug or study treatment(s) will be recorded in the patient file and subsequently in the eCRF.

All SAEs, will be fully documented in the appropriate eCRF. For each SAE, the investigator will provide the onset, duration, intensity, treatment required, outcome and action taken with the investigational product.

The intensity of SAEs will be assessed as being

- mild (hardly noticeable, negligible impairment of well-being),
- moderate (marked discomfort, but tolerable without immediate relief), or
- severe (overwhelming discomfort, calling for immediate relief).

The investigator will determine the relationship of the investigational drug to all AEs as defined on the AE page of the eCRF.

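### Protocol sections 10.2 and 10.3 give opposite rules on entering non-serious adverse events in the eCRF, so the database for the declared safety endpoint could be incomplete or inconsistent

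*Protocol*

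**What the plan says.** - **Section 10.2** states that AEs, whether seen by the investigator or mentioned by the patient, "must referring to the HFG, not be reported in the eCRF". The next sentence makes the exception: "All AEs, qualifying as an SAE , observed by investigator must be reported in the eCRF".
- **Section 10.3** covers "All observed or volunteered adverse drug events (serious or non-serious) and abnormal test findings, regardless of treatment group or suspected causal relationship", and has these entered first in the patient file and then in the eCRF. It closes by asking the investigator to judge the drug relationship of all AEs on an AE page of the eCRF.
- **Section 5.2.4** makes any AE or SAE a safety variable, and **section 6.3.3** states: "Adverse events (AE) or serious adverse events (SAE) will be actively sought and reported". Sections 6.4.3 and 6.4.4 call for AEs or SAEs to be recorded at visits 3, 4 and 5, and the study schedule marks AEs as the safety variable at the same visits.
- **Section 10.1** opens with "Serious adverse events occurring within the two study groups during the course of the study will be recorded". It then asks staff to report, and a study nurse to look through charts for, events of either kind.
- **Section 11.3** lists AEs among the items that source documents should contain.

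**The concern.** An investigator who sees a non-serious event has two instructions that cannot both be obeyed: following one section breaches the other. The trial names AEs, and not only SAEs, as its safety endpoint, so this decides whether the non-serious part of that endpoint reaches the trial database at all. Two hospitals enrol (section 7), and two investigators acting in good faith could fill the eCRF differently. A later analysis plan cannot repair this by itself, because it can only tabulate what was entered; anything else would have to be retrieved from the patient files.

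**Working it through.** The plan gives no figure on this point, so there is nothing numerical to reproduce. The check is a comparison of the text.

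**Step 1. Apply each section to each kind of event.**

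| Event | Section 10.2 | Section 10.3 | Agree? |
|---|---|---|---|
| SAE | in the eCRF | in the eCRF | yes |
| Non-serious AE | not in the eCRF | patient file, then eCRF | no |
| Abnormal test finding that counts as an AE but is not serious | not in the eCRF (the 10.2 definition of an AE includes abnormal laboratory findings) | patient file, then eCRF | no |

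The conflict is therefore limited to events that are not serious.

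**Step 2. See whether a softer reading removes it.**

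- The 10.2 sentence is garbled and could mean that AEs need not, rather than must not, be entered. Section 10.3 would still make entry mandatory, so the two rules would still differ.
- Section 10.3 speaks of adverse drug events, which might suggest drug reactions only. But the sentence applies whatever the "suspected causal relationship to the investigational drug or study treatment(s"), and the section ends by asking for causality of all AEs.
- Section 10.6 uses the AE page of the eCRF for SAE follow-up, so the existence of that page alone does not show that non-serious events belong on it. The explicit inclusion of non-serious events in 10.3 does.
- Section 10.2 appeals to the HFG. The abbreviation list in section 1 does not contain it, so the reader cannot settle the matter from the protocol.

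**Step 3. Look for a rule of precedence.** None was found. Sections 5.2.4, 6.3.3, 6.4.3 and 6.4.4 bring non-serious AEs into the endpoint but do not say where they are recorded. An entry in the patient file alone would satisfy them, so they do not themselves contradict 10.2. Section 10.1 names SAEs as recorded but does not say that only SAEs are, and its reporting and chart-review duties extend to non-serious events without saying where these are entered.

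**Result.** The contradiction lies between 10.2 and 10.3. The other sections show why it matters, and none of them resolves it.

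**The case against.** The best case for the plan is that little would be lost in practice. Section 10.2 bars eCRF entry only; sections 10.3 and 11.3 still put AEs in the patient file and source documents. A study nurse reviews charts after discharge (10.1), independent monitoring compares eCRFs with sources (11.1), and an internet-based secuTrial database serves the study (13). Both drugs are described as in routine use. This stands as mitigation: it makes a systematic split between the sites less likely. It does not tell the nurse or the monitor whether a non-serious event missing from the eCRF is an omission or correct practice.

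A reader might infer more than the text supports, in four ways:

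- *That no non-serious AE data would exist under 10.2.* Source records should remain; the gap is in the eCRF.
- *That a planned between-arm safety comparison is undermined.* Section 6.3.3 says that events are sought and reported and names no comparison. The hypotheses in 12.2 and the analyses detailed in 12.3 concern CTC levels.
- *That the arms would be affected differently*, because the attending anesthetist knows the allocation and is among those asked to report events. Section 8.6 keeps that person out of data collection and keeps the research team unaware of allocation until the final analysis. Nothing shows that capture would depend on arm.
- *That the loss can be sized from accrual.* Section 7 expects 5 to 10 patients a month at the university hospital and 3 to 8 at the second hospital. The second site's share could thus lie anywhere from 3/(3 + 10) = 23% to 8/(8 + 5) = 62%, although the remark that its rates are slightly lower makes the upper end less likely. Suppose the second site followed 10.2 entirely, the first followed 10.3 entirely, and event rates were equal. The pooled absolute rate in the eCRF would then be 1 − 0.62 = 38% to 1 − 0.23 = 77% of the true one. Risk ratios would be unchanged if capture did not depend on arm. Each of these conditions is an assumption, and the protocol does not say that the sites would diverge.

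**Conclusion.** The point holds as an internal contradiction on whether non-serious AEs are entered in the eCRF. Its consequence is that the trial database for the AE-or-SAE endpoint could be incomplete, or captured inconsistently between investigators or between the two sites. That is a possibility created by the text, not a demonstrated loss, and no single figure for its size can be defended from the document. SAE capture, the primary CTC analysis and the secondary variables are unaffected. The conclusion rests on both sections being current text and on no section giving either of them priority. It should be corrected, but it does not threaten the trial's main question.

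**What to change.** State one eCRF rule for non-serious AEs across sections 10.1 to 10.3 and make it agree with the endpoint. There are two consistent ways:

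1. **Keep the endpoint as declared.** Apply the 10.3 rule at both hospitals, delete the 10.2 sentence that keeps AEs out of the eCRF, and word the opening of 10.1 to cover AEs as well as SAEs. The cost is modest extra eCRF entry, since the listed AE recording runs from visit 3 at the end of surgery to visit 5 at 72 hours.
2. **Keep the eCRF to SAEs.** Restrict the safety variable and endpoint to SAEs in 5.2.4, 6.3.3, the visit lists in 6.4.3 and 6.4.4, and the study schedule. Delete the text in 10.3 that sends non-serious events to the eCRF and asks for causality of all AEs there. This needs less data entry, but the trial would then make no claim about non-serious events.

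In either case, spell out HFG if the reference is kept. Both are changes of wording. Section 13 requires an amendment signed by the Sponsor-Investigator and submitted to the ethics committee and Swissmedic, and both hospitals should be told which rule applies.
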